A Group-Based Walking Study to Enhance Physical Activity Among Older Adults: The Role of Social Engagement

Study Protocol and Statistical Analysis Plan

NCT03803085

Document Date: 7/22/2019

WeChat Study Protocol

Scientific background

There is compelling evidence that an active lifestyle has broad benefits for cognitive, physical, and psychological health among older adults (Cockerham, Wolfe, & Bauldry, 2020; Matz-Costa et al., 2016). Physical activity can delay or prevent many chronic diseases, including heart disease, type 2 diabetes, dementia, and some cancers (Booth et al., 2012). Active older adults have a reduced risk of moderate or severe physical limitations, are less likely to suffer from falls and fracturing bones, and are more likely to remain mobile and independent (Kohl et al., 2012; McPhee et al., 2016). Being physically and socially active can also improve mental health and delay dementia and cognitive decline (Holt-Lunstad et al., 2015; Liu & Lachman, 2019). According to the 2016 report from Centers for Disease Control and Prevention (CDC), non-institutionalized adults ages 50 years and older account for \$860 billion in health care costs each year, despite the fact that 4 in 5 of the most costly chronic conditions for this age group can be prevented or managed with physical activity (National Center for Health Statistics, 2017).

CDC researchers examined patterns of inactivity using data from the 2014 Behavioral Risk Factor Surveillance System for all 50 states and the District of Columbia (D.C.) and found 31 million Americans (28 percent) age 50 years and older were inactive, defined as no physical activity outside of work during the past month (Watson et al., 2016). Trends in physical activity consistently show that activity levels progressively decrease with age with the prevalence of inactivity being highest among adults aged 65 or greater. Current estimates indicate that 66% of adults over 75 do not engage in any

regular physical activity. Moreover, evidence suggests that 50% of sedentary adults have no plan of starting an exercise program (Watson et al., 2016).

In recent years, a number of researchers have conducted studies to evaluate the potential of using pedometers as health interventions (see Foster et al., 2010; Sullivan & Lachman, 2017). Foster and colleagues (2010) used pedometers and a specifically made app, StepMatron, on Facebook to compare the effects of social and non-social motivation on physical activity within a friend group in the same work place. The ten participants in the social group could see their step counts compared to their friends in a competitive format. The social group could also communicate with each other through the page. The nonsocial group could only see their own step counts and had no communication through the app with other participants. There was a significantly higher number of steps in the social group compared to the non-social group. The conversations of the participants in the social group indicated that the competitive social aspect among the friends influenced the number of steps. In a review of the evidence for increasing physical activity among sedentary adults using fitness technology, Sullivan and Lachman (2017) indicated that fitness technology, including trackers and smartphone applications, have become increasingly popular for measuring and encouraging physical activity. Overall, fitness technology has the potential to significantly impact public health, research, and policies. Behavior change techniques such as goal setting, feedback, rewards, and social factors are often included in fitness technology; however, it is not clear which components are most effective. Sullivan and Lachman (2017) discussed additional cognitive behavioral strategies not typically included in fitness technology devices or apps, such as action planning, restructuring negative attitudes, enhancing environmental conditions, and

identifying other barriers to regular physical activity, that were promising for engaging inactive populations. Our study adds to the discussion and considers social engagement as a possible mechanism for increasing physical activity among older adults using fitness technology.

The use of fitness technology services could have beneficial effects on chronic disease management in late life, including positive changes in health perception, social functioning, and mental health (Lindeman et al., 2020). Fitness technology is regarded as a vital means for maintaining and enhancing older people's quality of life (Khosravi et al., 2016; Mitzner et al., 2018). In addition, previous research also indicated that information communication technologies could provide a link between older adults and their informal and formal networks. Technologies allow older adults to transcend spatial barriers and provide them a greater sense of connection to other people (Clarke et al., 2009; Schlomann et al., 2020). Exploring the role of social factors in increasing physical activity using technology is a promising direction (Zhang et al., 2016).

Objectives

This paper reports on the use of WeChat to improve physical and social activity among community dwelling older adults. WeChat is a free mobile text and voice messaging communication service. This pilot study explored the efficacy of one function of the app WeChat: a group-based pedometer function WeRun. There are previous empirical studies conducted on WeRun with younger adults; for example, Gui and colleagues (2017) conducted a qualitative study of 32 users of WeRun. Their findings indicated that sharing fitness data with pre-existing social networks motivated users to continue self-tracking their steps and enhanced their existing social relationships.

However, we are not aware of any empirical studies conducted using WeRun with older adults.

The objectives of this study are to explore: a) whether the participants in the treatment group would show greater increases and higher maintenance of daily steps as well as greater increases in level of social engagement and exercise self-efficacy in comparison to the participants in the control group who were not given the treatment; and b) whether social engagement would be a significant mediator, that is a mechanism of behavior change.

Design

The study was approved by the University's Institutional Review Board. The clinical trial was registered at the US National Institutes of Health (ClinicalTrials.gov). After the participants were deemed eligible to participate in the study, participants were randomly assigned to one of two conditions: treatment or control. During the 4-week study, participants were blinded to condition. Data collection was also blinded to the experimenters, as the survey and physical activity data were collected through online platforms (Qualtrics and WeRun, respectively).

All participants completed a survey with demographic questions and the self-report outcome measures at pretest. They were asked to use WeRun to track their own daily steps for one week, prior to being assigned to groups. This provided pretest physical activity data and helped participants become familiar with WeChat and syncing the data with their phone. After 4 weeks of using the application, all participants completed the same self-report measures to assess changes in the outcomes of interest. They also completed a follow-up assessment 1 month after the post-test for the same measures.

During the intervention, participants' daily walking steps were recorded by WeRun, and the data were logged by the research assistant every day. The research assistant also recorded each participants' daily ranking and number of social interactions in the treatment condition. Messages were sent by email and WeChat messages to the participants to remind them to carry their phone with them as often as possible during the day and use the application every day. The trained research assistant explained how to use WeChat, WeRun to all participants. Participants in both conditions were asked to use the application every day. A message was sent to remind them to use the application if they had not done so for three consecutive days.

Treatment condition: Participants used WeChat for 4 weeks, during which time the steps data were recorded by the WeRun function and downloaded by the research assistants. The participants in the treatment condition could interact with the other group members by sending text messages which were documented by the research assistants. The researchers sent out instructions to check step counts on Monday mornings during the 4-week intervention, for example "Dear all, this is Week 1! please remember to take your phone with you as often as possible during the day and check your step count in WeRun by the end of the day. Please also share your number of steps with your group members. Thank you!" The daily walking steps of the participants in this group were displayed to the group and the participant with the highest daily steps in the group was indicated as the champion each day.

Control condition: Participants only saw their own daily walking steps using WeChat. They did not see other group members' daily steps and did not interact or compare walking steps with other group members. The participants received messages on

Monday mornings during the 4-week intervention to remind them to take their phones as often as possible during the day.

Methods

Participants

Eligibility. Inclusion criteria specified that participants must be 60 or older and fit enough to walk for at least 20 minutes at a time. They also needed to have a smartphone, with either an Android or iPhone system with Internet access. A power analysis (using G*Power 3.1) for the study and analysis design indicated that a total of 56 participants (randomly assigned across two groups) would provide adequate power ($> 80\%$) to detect medium-sized effects ($\rho = 0.3$) at $p < .05$. We recruited 60 participants in the northeast U.S. by posting recruiting posters in community public posting boards, including public libraries, grocery stores and shopping malls. Participants were given two 25-dollar gift cards (one at the pretest and one after the 4-week intervention) as compensation for their participation.

Sample. As shown in the consort diagram in Figure S1, of the 241 adults who filled out our eligibility questionnaire online, 38 were not eligible, 15 gave up as they had trouble downloading the app, 4 did not meet the age requirement, 4 indicating participating in a walking intervention would be a potential health risk, and 3 could not participate due to travel. One hundred and forty-three potential participants who were eligible did not respond when we notified them that they were eligible. Recruitment took place from October 2018 to March 2019, with primary data collection completed in February 2019, and follow-up data collection completed in March 2019. Those who were

physically active (i.e., who had 7,000 - 10,000 daily steps or above everyday) were not included after the one-week baseline. A total of 60 adults were recruited and randomly assigned to either the control condition ($n = 30$) or the treatment condition ($n = 30$). They completed the study in one of three subgroups, with 20 participants randomly assigned into two groups (10 in treatment group, and 10 in control group) for each subgroup.

Measures

Covariates. Age, gender, education, race, and self-reported health were used as covariates in the analyses because of their expected relationship with the outcome measures. For physical health, the participants were asked “in general would you say your health is?” The response options ranged from 1 (poor) to 5 (excellent) with a higher score indicating better physical health.

The outcome measures were administered at the pretest, posttest and follow up using self-report questionnaires given before and at the completion of week 4 of the pilot study and at the 1 month follow up through an online platforms-Qualtrics.

Daily step counts. Participants' daily steps were recorded by using the WeRun function in WeChat by the end of each day during the 4-week intervention period and at the 1 month follow up. Mean daily steps for pretest week, post-test week and one month follow up week were calculated as the mean number of steps across the 7 days in that week of the study.

Percentage change in mean weekly steps at posttest was calculated as the difference between the mean weekly steps at posttest and pretest divided by the mean weekly steps at pretest. The percentage change in mean weekly steps at the one month

follow up was calculated as the difference between the mean weekly steps at one month follow up and pretest divided by the mean weekly steps at pretest.

Social engagement. We had two measures of social engagement. The 18-item version of the Lubben Social Network Scale (LSNS), was used to examine social contact and support as indicators of social engagement at the pretest and posttests (Lubben & Gironda, 2004). For the treatment group only, the number of participants' daily text messages exchanged in the group discussion was used to measure social interaction. This version utilizes two subscales for friends and family and has the highest level of internal consistency ($\alpha = .82$) of the three available versions of the LSNS (Lubben & Gironda, 2004). The scale weighs size, closeness and frequency of social contacts. The sum of the 12 equally weighed items is computed with scores ranging from 0 to 60. Lower scores indicate smaller networks, or lower levels of perceived social support. Items include 'How many relatives (friends) do you see or hear from at least once a month?', 'How many relatives (friends) do you feel you can talk to about private matters?', and 'How many relatives (friends) do you feel close to such that you could call on them for help?'

Exercise self-efficacy. Based on Bandura's model (Bandura, 1990; Lachman et al., 2011; Resnick & Jenkins, 2000), exercise self-efficacy was measured using the Self-Efficacy for Exercise (SEE) Scale, which was a 9-item instrument that focuses on self-efficacy expectations related to the ability to continue exercising in the face of barriers to exercise. There was sufficient evidence of internal consistency ($\alpha = 0.92$), and a squared multiple correlation coefficient using structural equation modeling provided further evidence of reliability (R^2 ranged from 0.38 to 0.76). The sum of the nine items is computed with scores ranging from 0 to 90. Lower scores indicate lower levels of

exercise self-efficacy. Items include ‘the weather was bothering you’, “you were bored by the program or activity” and “you have to exercise alone”.

Data Analysis Plan

Statistical analyses of survey measures were done using SPSS. Descriptive information and correlations were computed for all study variables. Changes in daily steps, social engagement and exercise self-efficacy from the pretest to 4 weeks were examined. Repeated measures ANCOVA was used to test for effects of the treatment on mean daily step counts over the intervention period, exercise self-efficacy, and social engagement and to compare treatment and control groups at pretest, posttest, and follow-up using a two condition by three occasions design. All post hoc analyses were performed using Bonferroni corrections controlling the covariates. We conducted a sensitivity analysis without the covariates and the results were the same.

Conditional process modeling was applied using PROCESS in SPSS to test the predicted mediation model. Mediation analyses was based on 1000 bootstrapped samples using Hayes’ PROCESS Macro v3.3 (Hayes & Preacher, 2014), allowing for formal tests of the total, direct, and indirect effects of intervention on percentage of change of mean weekly steps from pre-test to post test. The predictor variable was condition, the mediator variable was change in social engagement, and the outcome was percent change in mean weekly steps from pre-test to post test.

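### The Design section claims blinding of staff and participants, but its own procedures show that research assistants knew the arm and participants knew which features they received

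*Combined protocol and SAP*

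**What the plan says.** The Design section makes two separate blinding claims: "During the 4-week study, participants were blinded to condition. Data collection was also blinded to the experimenters".

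- On participants, the sentence stands without a reason or qualification.
- On staff, the full statement adds its reason: "Data collection was also blinded to the experimenters, as the survey and physical activity data were collected through online platforms". The platforms named are Qualtrics for the surveys and WeRun for the steps. No other masking measure is described: no coded arm labels, no separate data handler and no sham group display.

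Later in the same section, on data handling during the intervention: "participants' daily walking steps were recorded by WeRun, and the data were logged by the research assistant every day". The next sentence reads: "The research assistant also recorded each participants' daily ranking and number of social interactions in the treatment condition".

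Under Treatment condition, research assistants download the steps and document the text messages that group members exchange. The researchers send a Monday message that includes "Please also share your number of steps with your group members". The display is described as follows: "The daily walking steps of the participants in this group were displayed to the group", with the person who walked most named as champion each day. Under Control condition, participants see their own counts only, have no contact or comparison with others, and receive a Monday reminder to carry the phone.

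Under Measures, social engagement (the Lubben scale) and exercise self-efficacy are questionnaires that participants complete online at pretest, posttest and follow-up. Steps are counted by WeRun. The Data Analysis Plan uses change in social engagement as the mediator between condition and percentage change in steps.

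**The concern.** Blinding is a stated property of the design, and readers use it to judge which biases can be set aside. Here the property is asserted in one paragraph, while the paragraphs that follow describe staff tasks and participant experiences that differ openly by arm.

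The stakes are highest for the questionnaires. When an outcome is self-reported, the participant is the assessor, and what the participant knows about the intervention can colour the answers. The intervention is a social, group-based feature, and one of the two scales measures social contact and support. That scale also carries objective (b), the test of social engagement as the mechanism of change. A reader who takes the Design section at face value would set aside expectation and reporting effects in exactly the results where they are most plausible.

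**Working it through.** No arithmetic applies. The plan gives no figure that depends on blinding, so there is nothing to reproduce. The check sets the claims against the procedures.

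**1. Staff.** The claim rests on one premise, that collection ran on online platforms. Three tasks bear on it:
- The research assistant logs daily steps (Design).
- The same role records ranking and social interactions for the treatment condition (Design).
- Research assistants document the treatment arm's messages (Treatment condition).

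A person who records rankings and messages for members of one arm knows who belongs to it. The platform governs how data arrive and does not hide the arm from the person who reads and logs them. The staff claim is therefore contradicted.

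**2. Participants.** Being blinded to condition could mean unaware of any of four things.

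| Unaware of | What the documents show |
|---|---|
| Features received | Contradicted: the group display, daily champion, messaging and request to share steps are all visible to those who get them; controls see own steps only |
| Arm label | Not contradicted |
| Existence of the other condition | Not contradicted: no procedure shows either arm what the other receives |
| Hypothesis | Not contradicted |

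The last three rows cannot be confirmed either. The text available does not say what participants were told, and consent pages are not part of it.

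**3. Which outcomes are exposed.** The plan tests three outcomes: daily steps, social engagement and exercise self-efficacy.
- Social engagement and self-efficacy are self-completed online, so 2 of 3 outcomes depend on participant awareness. Staff knowledge of the arm does not itself enter those answers.
- The mediator must be the Lubben score. The other social-engagement measure, the count of group messages, exists for the treatment group only and cannot be compared between conditions. The mediator is thus also self-reported.
- The indirect effect is the product of the condition-to-mediator path and the mediator-to-steps path. Any effect of awareness on reported social engagement would enter the first path.
- Steps are generated by the app. Knowledge of arm by the person logging them could act through transcription or through prompting that differs by arm. There is no assessor judgement for it to influence.

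**4. Who is affected.** The trial has 60 participants, 30 per arm. The group features apply to the 30 in treatment. The 30 controls knew they saw only their own counts, but nothing shows that they knew of the alternative.

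**The case against.** The strongest reply concerns participants. Both arms used the same app, were asked to use it daily and received Monday messages. Someone who has never heard of the other condition can know every feature on the screen and still not know whether it is the treatment or the control. On that reading the participant sentence may be true. This stands: the documents do not support the stronger inference, which a reader might draw, that participants knew their allocation. What does not stand is the unqualified sentence, since it does not say which kind of unawareness is meant and cannot cover the features received.

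Other inferences a reader might draw also go beyond the text:

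- **That the step outcome is compromised.** WeRun counts the steps, and no transcription error or unequal prompting is shown. Nor do the documents describe a hand log competing with a separate download, so there is no basis for preferring one source over the other.
- **That the bias favours treatment.** This is plausible, but no passage gives a direction. The sample Lubben items ask for numbers of relatives or friends and do not ask for an opinion of the programme.
- **That the assistant who logged steps also sent the arm-specific messages.** The treatment instructions are attributed to the researchers, and elsewhere the sender is not named.
- **That masking the analysis file would repair the problem.** Follow-up collection ended in March 2019 and the Data Analysis Plan already reports the outcome of a sensitivity analysis, so masked codes now could not blind work already done.

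It is also fair to say that no test, model or sample size changes, and that the Data Analysis Plan never invokes blinding. The point is therefore about what may be concluded from the results.

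**Conclusion.** The concern holds in a limited form. The staff-blinding claim is wrong as written, because it conflicts with the tasks the plan gives to research assistants. The participant claim can be true only of the label, the other condition or the hypothesis.

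The reach is two of three outcomes and the sole mediator. The size and direction of any bias are unknown and cannot be derived from the documents. For steps, what remains is a minor question about logging and prompting.

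The conclusion about staff assumes that the procedures were carried out as described and that no masking step was left unwritten. The conclusion about participants needs only the two condition descriptions. Infeasibility of full participant blinding in a trial like this is no criticism of the design; the fault lies in stating a protection that the procedures do not provide.

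**What to change.** Replace the two blinding sentences in the Design section with wording along these lines:

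*Research assistants who logged steps and documented group messages were aware of the arm. Participants were aware of the features they received. [Only if true: they were not told the label of their condition, the existence of the other condition, or the study hypothesis.]*

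Each item in the bracket should be kept only if the study records confirm it.

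In the report, describe the social-engagement, self-efficacy and mediation results as participant-reported and open to awareness of the intervention, and do not rely on blinding as protection against that bias. For steps, it is enough to say that counts came from the app and were logged by staff aware of the arm.

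The change is to text only: no data, model or analysis needs to be redone. The cost is a less favourable risk-of-bias statement.

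### Does the single power statement for 56 participants mislead about the mediation test of objective (b)?

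*Combined protocol and SAP*

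**What the plan says.** Methods, Participants (Eligibility) reads "A power analysis (using G*Power 3.1) for the study and analysis design indicated that a total of 56 participants", split at random over two groups, would give above 80% power for medium effects, expressed as rho = 0.3, at the 5% level. It does not identify the outcome, the model term, what rho measures, the sidedness, or any correlation between occasions. The Sample paragraph reports the number achieved: "A total of 60 adults were recruited and randomly assigned to either the control condition" or to treatment, 30 in each.

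The Objectives section has two parts. Part (a) compares the arms on steps, social engagement and exercise self-efficacy. Part (b) asks "whether social engagement would be a significant mediator, that is a mechanism of behavior change". The same section says "This pilot study explored the efficacy of one function of the app WeChat", and its lead-in to (a) and (b) describes both as matters to be explored.

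The Data Analysis Plan assigns a two-condition by three-occasion repeated-measures ANCOVA to (a) and a PROCESS mediation model to (b). For the latter, "Mediation analyses was based on 1000 bootstrapped samples", "allowing for formal tests of the total, direct, and indirect effects of intervention on percentage of change of mean weekly steps". The variables are set out: "The predictor variable was condition, the mediator variable was change in social engagement, and the outcome was percent change in mean weekly steps". The type of bootstrap interval is not given, and no separate power figure is given for this model.

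**The concern.** The power statement is said to cover the study and its analysis design, and the mediation model is part of that design. A reader could therefore take the 80% to apply to objective (b). An indirect effect is a product of two paths, and detecting it requires evidence on both. In addition, the second path links two change scores, one value each per participant, so it gains nothing from the three repeated occasions that may help the group comparison. An N that suffices for the arms need not suffice for mediation.

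What would be at stake is the reading of a null. If both paths were medium-sized, the test would miss a real mechanism about half the time or more. Someone relying on the 80% might then take an interval that includes zero as evidence that social engagement does not mediate.

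**Working it through.** **Inputs from the document.** N = 56 planned and 60 randomised, equal arms; rho = 0.3; alpha 0.05; three occasions; 1000 bootstrap samples; mediator and outcome as listed in the Data Analysis Plan.

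**Assumptions, because the document is silent.** Two-sided tests; between-occasion correlation r = 0.5; path sizes; no direct effect; normal errors; a 95% interval, either percentile or bias-corrected. Covariates (in the simulations), missing data and clustering within the groups of 10 are not modelled.

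**1. Can 56 be reproduced?** Convert rho to an effect size: f² = 0.09/0.91 = 0.0989, so f = 0.3145. For the between-condition effect averaged over m = 3 occasions, the noncentrality is lambda = N·f²·m/(1 + (m − 1)r).

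| N | lambda (r = 0.5) | Power |
|---|---|---|
| 54 | 54 × 0.0989 × 3/2 = 8.01 | 79.3% |
| 56 | 56 × 0.0989 × 3/2 = 8.31 | 80.8% |
| 60 | 60 × 0.0989 × 3/2 = 8.90 | 83.5% |

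With equal arms, 56 is the smallest total above 80%. The match depends on r: at N = 56, power is 84.7% for r = 0.4 and 77.0% for r = 0.6. A simple two-sided test of a condition–outcome correlation of 0.3 would need 82. So the figure fits a group comparison in the planned design. That is a plausible origin, not proof of what was run.

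**2. Second mediation path alone.** For a partial correlation of 0.3, lambda = N × 0.0989 with 1 and N − 3 degrees of freedom.

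- N = 56: lambda = 5.54, power 63.7%.
- N = 60: lambda = 5.93, power 66.8%.
- 80% power needs N = 82.

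**3. Indirect effect.** The first path is a condition–mediator correlation and the second is a partial correlation. A rough analytic check multiplies the powers of the two paths: 0.637 × 0.637 = 0.41 at 56 and 0.668 × 0.668 = 0.45 at 60. Simulation with 5000 trials per cell and 1000 resamples gives:

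| First path, second path | N = 56, percentile / bias-corrected | N = 60, percentile / bias-corrected |
|---|---|---|
| 0.3, 0.3 | 38% / 50% | 42% / 55% |
| 0.353, 0.3 | 48% / 59% | 52% / 63% |
| 0.3, 0.5 | 65% / 72% | 68% / 73% |
| 0.8, 0.3 | 63% / 64% | 67% / 68% |
| 0.353, 0.5 | 79% / 83% | 82% / 86% |

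With the first path at 0.5 and the second at 0.3, the bias-corrected figures are about 69% and 71%. For that interval type, then, power does not rise steadily with the first path, and the single-path power in step 2 is not a strict ceiling. With both paths at 0.3, about 110 participants would be needed for 80% with a percentile interval.

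**4. Comparing result with claim.** Step 3 shows low power under one plausible scenario. It contradicts the plan only if the plan claims 80% for the indirect effect, and it does not. The sentence continues "indicated that a total of 56 participants (randomly assigned across two groups", which is the language of a comparison between arms, and step 1 shows that such a comparison accounts for the number.

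**The case for a change.** The best case for a change is that both readings of the power sentence leave a fault. If it covers mediation, it is wrong at rho = 0.3. If it does not, one of two stated objectives has no power basis and the plan is silent on it. Significance language in the Objectives and formal testing in the Data Analysis Plan sound confirmatory. A sentence or two would settle the matter at almost no cost.

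Part of this stands. The powered term should ideally have been named, the mediation test has no calculation of its own, and power with two paths of 0.3 is well short of 80%. Other readings of 0.3 (standardised coefficients, or all three simple correlations at 0.3) give 25% to 57%, so the direction does not depend on one parameterisation.

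The inference to a defect does not stand. The second reading is the natural one, and a pilot need not power a mechanistic question separately. Nor can the effect behind the 56 be carried over to the mediation paths. Step 1 needs the difference to hold on average over all three occasions. If it arose only after pretest, the average would be two-thirds as large, lambda at 56 would be 8.31 × 4/9 = 3.69, and power would be about 47%. Both paths at 0.3 is therefore a free assumption, and the tabulated scenarios run from 38% to 86%.

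**Conclusion.** No change to the plan follows. The 56 is not shown to be wrong: it is recovered at 80.8% for the between-condition effect in the two-by-three design, given r = 0.5. The low mediation power (38% to 55% at 56 to 60 participants with both paths at 0.3) is real under its assumptions, but no statement in the plan conflicts with it.

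The harmful step, reading a null indirect effect as absence of mediation, is not one the plan takes. The Objectives already describe (b) as exploratory within a pilot. The bootstrap analysis produces an interval for the indirect effect, and its width will show how little a null result says. Analysts can be expected to report that interval with its type and to discuss it as exploratory.

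The gain from a revision would be small. The Sample paragraph puts the end of follow-up in March 2019 and the document is dated July 2019, so N cannot respond to the point. Naming the powered term and its inputs would improve the record, but the sample size, the ANCOVA, the mediation model and the number of resamples would all stay the same. This is missing detail in the power description, not an error in the design or analysis.
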